Specifically, populations are defined as follows, supported by the chart (**Table 3**) evaluating the impact of each type of treatment switching on the analysis.

Populations were defined considering all possible types of treatment switching in a blinded fashion without knowing if particular treatment switch scenarios occurred. As such, although all scenarios were considered, planned sensitivity analyses are specified a priori to be conducted only if there are at least 6 participants whose inclusion or values will be impacted by implementing that analysis. Six was selected prior to data unblinding since if a treatment group had 6 such issues, 6 is 5% of the planned 120 participants per treatment arm. In addition, if the MITT-narrow population is identified as only being 2 or fewer patients smaller than the MITT population, then the benefit of applying the MITT-narrow population definition is a priori considered to be outweighed by the benefit of instead using the MITT population in place of the MITT-narrow population in order to achieve results that are substantially easier to present and interpret. After database lock and unblinding, but prior to conducting any efficacy analyses, the population sizes will be evaluated and any such evaluations that

deemed not to be done or to use a different analysis population based on these sample size rules will be documented. Two was selected prior to data unblinding as a very small number unlikely to impact analysis at a level that would warrant the complexities of having a separate analysis population.

**MITT:** all randomized patients, excluding patients who discontinued the study without having surgery. Treatment switchers are included in the treatment to which they were randomized.

[figure not shown]
**MITT- narrow**: all randomized patients, excluding patients who discontinued the study without having surgery and patients randomized to receive SC but received TM or vice-versa (randomized to TM but received SC). This is a subset of MITT. Treatment switchers are included in the treatment to which they were randomized.

**Per Protocol**: all randomized patients excluding all major protocol violations related to treatment including patients who discontinued the study without having surgery, all patients with treatment-related protocol violations, and all patients who did not receive their randomized treatment. This is a subset of the MITT-narrow.

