#### Analysis Populations used for Analysis of the primary outcome (time to treatment failure), including sensitivity analyses

Populations to be used in the analyses for the primary and secondary efficacy outcomes are summarized in Table 2:

Table 2 Summary	of Analysis Populatio	ns
------------------------	-----------------------	----

	Primary Efficacy					
Туре	Aim 1Aim 1aNon-inferiority of TVM to SCSuperiority of TVM to SC		Aim 2 Superiority of TVM to NTR	Aim 3 Superiority of SC to NTR	All Secondary Efficacy Outcomes	
Primary	Per-Protocol	MITT	MITT-narrow	MITT-narrow	MITT	
Sensitivity	Aim 1 PP Sensitivity Pop					
Supportive	MITT	Per-Protocol	MITT and Per-Protocol	MITT and Per-Protocol	Per-Protocol	

Aim 1 (non-inferiority of TM to SC):

- The primary analysis will be conducted on the **per-protocol** population.

- A supportive secondary analysis will be conducted on the **MITT** population.
- Sensitivity analyses of the primary analysis will add patients to the per-protocol population who were randomized to TM but who (A) were never treated (imputed as failures with time to failure = 6 months), or (b) were switched during surgery from TM to NTR (A1PPS population). Each sensitivity analysis will only be completed if the additional patients add up to at least 5 patients.

Aim 1a (If TM is found to be non-inferior to SC, then a step-down comparison will evaluate superiority of TM to SC):

- The primary analysis will be conducted on the **MITT** population.
- A supportive secondary analysis will be conducted on the **Per-Protocol** population.
- A sensitivity of the primary analysis will add patients to the MITT population who were randomized to SC or TM but who were never treated (imputed as failures with time to failure = 6 months). Sensitivity analysis will only be completed if the additional patients add up to at least 5 patients.

Aims 2 and 3 (superiority of SC to NTR and superiority of TM to NTR):

- The primary analysis will be conducted on the **MITT-narrow** population.
- A supportive secondary analysis will be conducted on the **Per-Protocol** population, and also on the **MITT** population.

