- A sensitivity of the primary analysis will add patients to the MITT-narrow population who were randomized to SC or TM but were never treated (imputed as failures with time to failure = 6 months). Sensitivity analysis will only be completed if the additional patients add up to at least 5 patients in either the SC or the TM treatment group.

All secondary efficacy evaluations will be analyzed on the **MITT** population (primary) and also on the **Per-Protocol** population (supportive).

Safety Evaluations:

- All safety analyses will be conducted on the safety population (with selected switchers presented as treated).

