#### Pelvic Floor Disorder

For a sensitivity analysis , to be conservative, we should assume they did not get surgery for a reason related to the type of surgery (Biased) and impute a worst outcome. This sensitivity analysis will only be done if there are at least 6 participants in this category in a treatment group.	Do a sensitivity analysis adding TM cases only to the primary PP analysis as failure at 6 months to test if TM is NI to SC cases – this stacks the deck in favor of SC.	Do a sensitivity analysis adding SC and TM cases only to the primary MITT analysis, as failures. This does not stack the deck in favor of either treatment group.	Do a sensitivity analysis adding SC and TM cases only to the primary MITT-narrow analysis, as failure at 6 months - this stacks the deck in favor of NTR (presumed to be the worst treatment)
Randomized but received AN AI	LTERNATE protocol treatment at	MD discretion (cases 4-6):	
4 . NTR switched to TM or SC This should never happen, as NTR should never be contra- indicated. Switching would be BIASED as other 2 treatments are expected to be superior	N/A (exclude from PP pop definition)	N/A (include in MITT definition)	INCLUDEThis is assumed to be conservative as switch is expected to improve outcome of NTR and thus make planned superiority comparison tougherSecondary Supportive analysis: EXCLUDE from a PP analysis
5. SC or TM switched to NTR	EXCLUDE	INCLUDE	INCLUDE
Although the protocol did not specify a plan of what to do if SC or TM could not be done, including switchers in the ITT defines the primary hypothesis to compare "start out planning	Major protocol violation, it is assumed this would make the outcome worse for the switcher and muddy the comparison.	This is intent-to-treat, or ICH E9R1 "treatment policy" and compares the treatments as they were planned to be.	This is assumed to be conservative as switch is expected to worsen outcome of SC/TM and thus make planned superiority comparison tougher.

Pelvic Floor Disorder

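### SAP section 5 gives conflicting triggers (5 or 6 women, summed or per arm) for the sensitivity analyses on never-operated and switched women

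*SAP*

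**What the plan says.** Section 5 of the SAP states the trigger six times.

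| Place in SAP section 5 | Women concerned | Minimum | Counted over |
|---|---|---|---|
| Opening text | any planned sensitivity analysis | 6 | participants affected |
| Aim 1 text | untreated TVM; TVM-to-NTR switchers | 5 | women added (TVM only) |
| Aim 1a text | untreated SC and TVM | 5 | SC and TVM together |
| Aims 2 and 3 text | untreated SC and TVM | 5 | either arm |
| Table 3, row 3 | untreated, all aims | 6 | one treatment group |
| Table 3, row 5 | TVM-to-NTR switchers, Aim 1 | 6 | women added back |

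The opening text has these analyses "conducted only if there are at least 6 participants whose inclusion or values will be impacted by implementing that analysis" and explains its choice of six: "since if a treatment group had 6 such issues, 6 is 5% of the planned 120 participants per treatment arm". For Aim 1 the wording is "Each sensitivity analysis will only be completed if the additional patients add up to at least 5 patients", and Aim 1a repeats that rule for SC and TVM women taken together. For Aims 2 and 3 the analysis will "only be completed if the additional patients add up to at least 5 patients in either the SC or the TM treatment group". Table 3, row 3, which covers all aims, says: "This sensitivity analysis will only be done if there are at least 6 participants in this category in a treatment group".

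On timing: "After database lock and unblinding, but prior to conducting any efficacy analyses, the population sizes will be evaluated". The same passage calls the rules a priori and requires that analyses dropped under them be documented.

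**The concern.** The same data can require a sensitivity analysis under one sentence and omit it under another. Because the counts are looked at after unblinding, whoever settles the conflict will know the counts by arm.

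What is at stake differs between the two groups of women. MITT, MITT-narrow and per-protocol all leave out women who were randomised but never operated on. For them the triggered analyses are the only ones in the SAP that bring them back, imputed as failures at 6 months. For Aim 1 this is the direct stress test of the non-inferiority claim, since only TVM women are added and all as failures. TVM-to-NTR switchers are less exposed, because they also return through an analysis that has no trigger.

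**Working it through.** **1. The SAP's own figure.** 6/120 = 5.0%, as stated. On the planned 121 per arm, 6/121 = 4.96%. The other threshold gives 5/120 = 4.2%. The stated reason therefore supports 6 and not 5, and it is a per-arm reason.

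**2. Where the rules disagree.** Let s and t be the numbers of affected SC and TVM women.
- Aim 1 (TVM only): 5 against 6. They conflict at t = 5, separately for untreated women and for TVM-to-NTR switchers. Summed and per-arm counts coincide here.
- Aim 1a: s + t ≥ 5 (text) against max(s, t) ≥ 6 (Table 3, row 3). They conflict whenever s + t ≥ 5 with both at most 5. Of the 36 pairs with both between 0 and 5, 15 have a total of 4 or less, so 36 − 15 = 21 pairs conflict. Example: 4 and 4 gives a total of 8, so the text says run it; no arm reaches 6, so Table 3 says do not.
- Aims 2 and 3: max(s, t) ≥ 5 against max(s, t) ≥ 6. They conflict when the larger arm has exactly 5 (6 + 6 − 1 = 11 pairs). If the opening rule is read as a sum, 6 further pairs conflict: both arms at 4 or fewer and a total of at least 6.

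**3. Does a count of 5 matter for Aim 1?** Inputs from SAP section 6: 2-year success 80% in both mesh arms, so hazard λ = −ln(0.80)/2 = 0.1116; 5% yearly loss, so δ = −ln(0.95) = 0.0513; 2 years of recruitment plus 3 of follow-up, so 3 to 5 years of observation, taken as uniform; margin 1.93, ln = 0.6575; one-sided alpha 0.03, z = 1.881.

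Probability of an observed failure: λ/(λ+δ) × [1 − exp(−(λ+δ)F)], averaged over F from 3 to 5 years = 0.3264.

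*Reproducing the planned power.* 2 × 121 × 0.3264 = 79.0 events; SE = √(4/79.0) = 0.2250; 0.6575/0.2250 − 1.881 = 1.041, so power is 85%, as the SAP states.

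*Base case.* SAP section 6 expects TVM at about 95% of plan: 0.95 × 121 = 115 women. Events: 115 × 0.3264 = 37.5 TVM and 121 × 0.3264 = 39.5 SC. SE = √(1/37.5 + 1/39.5) = 0.2280; 0.6575/0.2280 − 1.881 = 1.003, so 84%.

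*Adding 5 TVM failures at 6 months.* TVM exposure is 37.5/0.1116 = 336 woman-years. New TVM rate: (37.5 + 5)/(336 + 5 × 0.5) = 0.1256. Hazard ratio: 0.1256/0.1116 = 1.125, ln = 0.118. SE = √(1/42.5 + 1/39.5) = 0.2210. (0.6575 − 0.118)/0.2210 − 1.881 = 0.56, so 71%.

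*Simulation* of 40,000 trials on the same assumptions: non-inferiority shown in 84.1% without and 71.3% with the 5 women. The difference, 12.8 points, is the share of all trials that lose the finding. Among trials that had shown it, the share is 12.8/84.1 = 15%. Four added women reverse about 10% of all trials and three about 7%.

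**The case against.** The strongest reply is that this is a drafting slip in secondary analyses. Several parts of that reply stand.

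- *Timing.* A reader might infer that analyses are picked once results are known. The SAP does not support that: six is said to have been chosen before unblinding, the counts are applied before any efficacy analysis, and omissions are documented. With one consistent rule, the step would leave almost nothing to decide. The discretion comes only from the conflict.
- *Switched women.* A reader might infer that TVM-to-NTR switchers vanish if the trigger is not met. They do not. The supportive MITT analysis for Aim 1 includes them with no minimum count, and the primary populations for Aims 1a, 2 and 3 already contain them. What would be lost is the Aim 1 per-protocol sensitivity (A1PPS) analysis, the only one that adds TVM switchers alone.
- *Counting unit.* The per-arm reason given for six suggests that the opening rule means the same as Table 3, row 3. On that reading the clear conflict of unit is confined to Aim 1a; the 5-versus-6 conflict remains everywhere.
- *Size.* The fall from 84% to 71% might be read as lost power for the trial. It is not. The claim rests on the per-protocol analysis, and the added women are a deliberate worst case. In a trial with an observed hazard ratio of exactly 1, adding 5 gives an upper 94% limit of 1.125 × exp(1.881 × 0.2210) = 1.70, still below 1.93. The reversals come from sampling variation around that value.

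None of this says which of the stated rules applies.

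**Conclusion.** The triggers conflict on the face of the text, in number throughout and in counting unit for Aim 1a, and nothing in section 5 ranks them. The consequence is limited to whether certain sensitivity analyses are run and reported; these triggers do not change any primary test, alpha level or margin. It should be fixed all the same, because for never-operated women these are the only analyses that restore them, and 5 such TVM women can matter: about 13% of all trials, or 15% of those showing non-inferiority, would lose that result in the stress test. Those figures assume equal exponential hazards at the design value, 5% yearly loss, uniform 3 to 5 years of follow-up, 115 TVM and 121 SC women, and a rate-based log hazard ratio in place of the planned piecewise model. The documents do not give the actual numbers of untreated or switched women, so whether a conflicting count arises is unknown.

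**What to change.** Preferred: remove the count conditions. Run each listed untreated-patient analysis and the A1PPS analysis whatever the count, and report the number of women added per arm beside each result.

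If a trigger is kept, state one number and one counting unit, in the same words, in the opening text, the Aim 1 and Aim 1a text, the Aims 2 and 3 text, and Table 3, rows 3 and 5. The rule must be fixed before unblinding. The count itself may have to follow, because a per-arm count needs the randomised arm, which a masked review does not show; with a single rule that later count leaves no choice. SAP section 12 (Version 2) already reports events by arm and does not touch the triggers, so from that version on only the first option avoids a choice made with the arms known.

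Cost: a few lines of SAP wording and a few extra model runs, on populations already defined, for the supplement.

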#### Analysis Populations used for Analysis of the primary outcome (time to treatment failure), including sensitivity analyses

Populations to be used in the analyses for the primary and secondary efficacy outcomes are summarized in Table 2:

Table 2 Summary	of Analysis Populatio	ns
------------------------	-----------------------	----

	Primary Efficacy					
Туре	Aim 1Aim 1aNon-inferiority of TVM to SCSuperiority of TVM to SC		Aim 2 Superiority of TVM to NTR	Aim 3 Superiority of SC to NTR	All Secondary Efficacy Outcomes	
Primary	Per-Protocol	MITT	MITT-narrow	MITT-narrow	MITT	
Sensitivity	Aim 1 PP Sensitivity Pop					
Supportive	MITT	Per-Protocol	MITT and Per-Protocol	MITT and Per-Protocol	Per-Protocol	

Aim 1 (non-inferiority of TM to SC):

- The primary analysis will be conducted on the **per-protocol** population.

- A supportive secondary analysis will be conducted on the **MITT** population.
- Sensitivity analyses of the primary analysis will add patients to the per-protocol population who were randomized to TM but who (A) were never treated (imputed as failures with time to failure = 6 months), or (b) were switched during surgery from TM to NTR (A1PPS population). Each sensitivity analysis will only be completed if the additional patients add up to at least 5 patients.

Aim 1a (If TM is found to be non-inferior to SC, then a step-down comparison will evaluate superiority of TM to SC):

- The primary analysis will be conducted on the **MITT** population.
- A supportive secondary analysis will be conducted on the **Per-Protocol** population.
- A sensitivity of the primary analysis will add patients to the MITT population who were randomized to SC or TM but who were never treated (imputed as failures with time to failure = 6 months). Sensitivity analysis will only be completed if the additional patients add up to at least 5 patients.

Aims 2 and 3 (superiority of SC to NTR and superiority of TM to NTR):

- The primary analysis will be conducted on the **MITT-narrow** population.
- A supportive secondary analysis will be conducted on the **Per-Protocol** population, and also on the **MITT** population.
- A sensitivity of the primary analysis will add patients to the MITT-narrow population who were randomized to SC or TM but were never treated (imputed as failures with time to failure = 6 months). Sensitivity analysis will only be completed if the additional patients add up to at least 5 patients in either the SC or the TM treatment group.

All secondary efficacy evaluations will be analyzed on the **MITT** population (primary) and also on the **Per-Protocol** population (supportive).

Safety Evaluations:

- All safety analyses will be conducted on the safety population (with selected switchers presented as treated).

#### Table 3. Definition of analysis populations for patient groups based on status of treatment received

Comparison	Aim 1: Primary Non-Inferiority: TM Non-Infer. to SC	Aim 1A: Step-down Superiority SC vs TM (2-sided)	Aims 2 and 3: Primary Superiority: SC vs NTR, TM vs NTR (2-sided)		
Population:	Per-Protocol (PP)	Modified ITT (MITT)	Modified ITT (MITT) - Narrow		
1. Randomized and treated with no major protocol violations	INCLUDE	INCLUDE	INCLUDE		
2. Randomized and treated, but the assigned study treatment was substantially modified or not completed, or there was some other major protocol violation related to the STUDY treatment (However,	EXCLUDE Standard guideline is to exclude modifications and violations which could muddy true treatment differences.	INCLUDE	INCLUDE		
there was NO switch to one of the other 2 study treatments)	Secondary Supportive analysis: INCLUDE in MITT analysis (as planned is a relevant secondary question)	Secondary Supportive analysis: EXCLUDE in Per- Protocol analysis	Secondary Supportive analysis: EXCLUDE in Per-Protocol analysis		
3 . Randomized and withdrew pre-surgery: women with no surgery and no follow-up info	EXCLUDE Sensitivity analysis:	EXCLUDE Sensitivity analysis:	EXCLUDE Sensitivity analysis:		

#### Pelvic Floor Disorder

For a sensitivity analysis , to be conservative, we should assume they did not get surgery for a reason related to the type of surgery (Biased) and impute a worst outcome. This sensitivity analysis will only be done if there are at least 6 participants in this category in a treatment group.	Do a sensitivity analysis adding TM cases only to the primary PP analysis as failure at 6 months to test if TM is NI to SC cases – this stacks the deck in favor of SC.	Do a sensitivity analysis adding SC and TM cases only to the primary MITT analysis, as failures. This does not stack the deck in favor of either treatment group.	Do a sensitivity analysis adding SC and TM cases only to the primary MITT-narrow analysis, as failure at 6 months - this stacks the deck in favor of NTR (presumed to be the worst treatment)
Randomized but received AN AI	LTERNATE protocol treatment at	MD discretion (cases 4-6):	
4 . NTR switched to TM or SC This should never happen, as NTR should never be contra- indicated. Switching would be BIASED as other 2 treatments are expected to be superior	N/A (exclude from PP pop definition)	N/A (include in MITT definition)	INCLUDEThis is assumed to be conservative as switch is expected to improve outcome of NTR and thus make planned superiority comparison tougherSecondary Supportive analysis: EXCLUDE from a PP analysis
5. SC or TM switched to NTR	EXCLUDE	INCLUDE	INCLUDE
Although the protocol did not specify a plan of what to do if SC or TM could not be done, including switchers in the ITT defines the primary hypothesis to compare "start out planning	Major protocol violation, it is assumed this would make the outcome worse for the switcher and muddy the comparison.	This is intent-to-treat, or ICH E9R1 "treatment policy" and compares the treatments as they were planned to be.	This is assumed to be conservative as switch is expected to worsen outcome of SC/TM and thus make planned superiority comparison tougher.

Pelvic Floor Disorder

to do SC" versus "start out planning to do TM" Note that NT is expected to have worse outcome.	Sensitivity analyses: 1: Do a sensitivity analysis INCLUDING these cases in the primary PP analysis for TM group only (excluding the SC cases only), to see if it is NI to per-protocol SC cases – this stacks the deck in favor of SC. This sensitivity analysis will only be done if there are at least 6 participants in this category to add back. Secondary Supportive analysis: Include both groups in MITT analysis. (as-planned is a relevant secondary question)	Secondary supportive analysis : EXCLUDE in a PP analysis	Secondary Supportive analysis: EXCLUDE both from a PP analysis
6. SC switched to TM	EXCLUDE	INCLUDE	EXCLUDE
or TM switched to SC The protocol did not specify a plan of what to do if SC or TM could not be done. Since the switching to another treatment was surgeon preference, then the outcome for switchers must be considered biased, and primary analysis is focused on "as-treated".	This is a straightforward major protocol violation for the non- inferiority analysis. Since the primary goal of the trial is to compare TM to SC, switching muddies that comparison Secondary Supportive analysis: Include both groups in MITT analysis. As-planned is a relevant secondary evaluation	This is conservative as switch makes superiority comparison tougher Secondary supportive analysis : EXCLUDE in a Per Protocol analysis	Although SC and TM MIGHT be similar, they also might not, and so mixing up the groups would not be appropriate for understandable estimates of treatment effect vs NTR. Therefore, these cases are excluded from the MITT-narrow in primary comparison with NTR Secondary supportive analysis: INCLUDE these cases for an "as- planned" analysis using the MITT population

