Because randomization occurred prior to scheduling the surgery, some randomized patients did not receive surgery. Also, during surgery some patients were determined by the surgeon to be inappropriate candidates to receive the randomized surgery due to anatomic or other contraindications discovered at the time of the surgery and undeterminable prior to surgery. In these cases, the surgeon selected amongst the other two study surgeries based on physician preference.

Evaluations for superiority will follow a modified intent-to-treat (MITT) approach, and evaluations of non-inferiority will follow a per-protocol approach, which is the customary conservative approach for non-inferiority hypotheses.

To define the MITT population, the intent-to-treat population is modified to remove patients who were randomized but never received surgery due to patient-specific reasons unrelated to the randomized treatment.

The per-protocol population is the subset of the modified intent-to-treat population excluding all major protocol violations related to study treatment including receipt of a treatment other than the randomized treatment.

Safety data will be evaluated for the safety population that will exclude randomized participants who discontinued the study without having surgery and participants who received a non-study surgery rather than one of the three study surgeries. Treatment switchers will be included in the treatment they received.

M.3. Statistical Data Analysis

Both for the overall global test across cohorts and within each of the three cohorts, surgical failure rates will be compared using survival analysis approaches appropriate for interval censored data (e.g. interval censored piecewise proportional hazards models) and secondary outcomes will be reported as rates in each group or as group means and evaluated

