The concept was approved by the PFDN Steering Committee on October 11, 2013, mini-protocol on January 17, 2014, and the full protocol was initially approved on April 25, 2014. Version 1.0 of the protocol was approved on November 24, 2015, after review by the DSMB and the Steering Committee.

- The protocol was first amended (Version 2.0) on January 27, 2016, to add Elevate as one of the allowed types of transvaginal mesh and update text to be consistent with an FDA order in January 2016 which reclassified transvaginal mesh devices from class II (moderate-risk) to class III (high-risk).
- A new version, 3.0, of the Protocol was issued on December 5, 2016, to remove the Elevate device as a mesh surgery option because the company manufacturing the kits halted production in March 2016 and went out of business, add University of Texas at Southwestern as a clinical site, and remove the Functional Activity Scale, PFDI-20, and BIPOP assessments from the 6 week time point.
- Version 4.0 (December 27, 2018) updated the target enrollment to randomized and treated participants, added a step-down test of superiority of TVM to SC if TVM is found non-inferior to SC, and defined the primary analysis populations (MITT for superiority, Per protocol for non-inferiority).

The protocol was updated to Version 5.0 on April 18, 2019, in response to FDA action. On April 16, 2019, the FDA issued a notification that required all manufactures of transvaginal mesh for prolapse repair to stop selling and distributing the product. Following the FDA notification, the Steering Committee along with the NICHD and DSMB felt that it would be unreasonable to continue with

enrollment of patients into the TVM arm of the trial. Thus, the TVM arm was halted at this time. All participants including those who received TVM were continued to be followed as recommended by the FDA and PFDN Steering Committee. Participants who were randomized to receive TVM were notified of the FDA statement and recommendation for follow up.

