#### 5 ANALYSIS POPULATIONS

Because randomization occurred prior to scheduling the surgery, some randomized patients did not receive surgery. Also, during surgery some patients were determined by the surgeon to be inappropriate candidates to receive the randomized surgery due to anatomic or other contraindications discovered at the time of the surgery and undeterminable prior to surgery. In these cases, the surgeon selected amongst the other two study surgeries based on physician preference.

Evaluations for superiority will follow a modified intent-to-treat (MITT) approach, and evaluations of non-inferiority will follow a per-protocol approach, which is the customary conservative approach for non-inferiority hypotheses.

To define the MITT population, the intent-to-treat population (all randomized participants) is modified to remove patients who were randomized but never received surgery.

The per-protocol population is the subset of the modified intent-to-treat population excluding all major protocol violations related to study treatment, which might be receipt of a treatment other than the randomized treatment and might be another type of violation.

In addition, given that some patients received a treatment selected by the physician when their randomized treatment was contra-indicated, the MITT and Per-protocol populations were further refined so that treatment switches that were conservative against the null hypothesis are included in the population, and treatment switches that might make the comparison biased against the null are excluded (see below).

Safety data will be evaluated for the safety population that will exclude randomized participants who discontinued the study without having surgery. Participants who received an alternate surgery (treatment switch) after an intraoperative complication or medical contraindication or received a type of surgery other than one of the 3 study treatments will be presented by their randomized (index) surgery. Participants whose treatment was switched prior to surgery or very early during surgery with no initial intraoperative complication caused by the randomized (index) surgery or medical contraindication for the selected surgery (i.e. participant refusal or accidental switch) will be presented by their switched final procedure they received in safety displays. Such participants will be identified by study PI review prior to database lock.

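### For Aims 2 and 3 the SAP replaces the protocol's MITT with MITT-narrow, which drops women switched between the two mesh operations after randomisation and so takes them from the mesh arms only

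*SAP*

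**What the plan says.** Protocol M.2 states: "Evaluations for superiority will follow a modified intent-to-treat (MITT) approach". To form that population it removes only "patients who were randomized but never received surgery due to patient-specific reasons unrelated to the randomized treatment". Receiving an operation other than the one assigned is an exclusion only for its per-protocol set. SAP section 1 records that protocol Version 4.0 "defined the primary analysis populations (MITT for superiority, Per protocol for non-inferiority").

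SAP section 5 then refines the populations. Its general rule is that "treatment switches that might make the comparison biased against the null are excluded". For Aims 2 and 3 it says: "The primary analysis will be conducted on the MITT-narrow population". MITT becomes supportive. Table 3 of section 5 (the table of population definitions) sorts switchers as follows for Aims 2 and 3:

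- Row 4, native tissue switched to either mesh operation: kept, as randomised.
- Row 5, either mesh operation switched to native tissue: kept, as randomised.
- Row 6, colpopexy switched to transvaginal mesh or the reverse: "these cases are excluded from the MITT-narrow in primary comparison with NTR".

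If MITT-narrow is smaller than MITT by two or fewer women, MITT is used instead. On timing: "After database lock and unblinding, but prior to conducting any efficacy analyses, the population sizes will be evaluated". SAP section 9.4 repeats MITT for superiority and adds that some switchers are removed. SAP Table 2 swaps the labels of Aims 2 and 3 relative to the objectives, but both use MITT-narrow, so this point is unaffected.

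**The concern.** The two documents name different primary populations for two of the three primary hypotheses, each tested at two-sided 0.01. If the results differ across that threshold, the protocol and the SAP give different answers.

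The difference matters because of how women leave the population. Protocol M.2 says that when a contraindication was found during surgery, "the surgeon selected amongst the other two study surgeries based on physician preference". A switch is therefore a post-randomisation event that may be related to prognosis. A woman randomised to native tissue who had the same hidden feature would not be revealed by it, and the SAP expects native tissue never to be contraindicated. Row 6 can thus take women only from the colpopexy and transvaginal mesh arms, leaving the remaining mesh women to be compared with an unselected native tissue arm.

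**Working it through.** **Design figures.** Protocol M.1 and SAP section 6 give 121 per arm, 2-year success of 80% (mesh) and 60% (native tissue), 2-year accrual, 3 further years of follow-up, and 5% loss per year. The exponential hazards are −ln(0.80)/2 = 0.1116 and −ln(0.60)/2 = 0.2554, matching the documents. Their ratio, native tissue to mesh, is 2.289. With loss hazard −ln(0.95), the event probabilities are 0.3264 and 0.5847, so expected events are 121 × (0.3264 + 0.5847) = 110.2. Schoenfeld power at two-sided 0.01 is Φ(ln 2.289 × √(110.2/4) − 2.576) = 96.2%, consistent with the stated figure of more than 93%.

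**Effect on power.** Drop 6 women from one mesh arm, unrelated to outcome. Events become 115 × 0.3264 + 121 × 0.5847 = 108.3, the mesh share is 115/236, and power is 95.8%. The issue is bias, not power.

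**Effect on the hazard ratio.** The documents give no count of mesh-to-mesh switchers, so assume 6 of 121 (5%), all from the colpopexy arm. Hold true 2-year failure at 20% in the whole colpopexy arm (24.2 expected failures) and 40% in native tissue. With d failures among the six, the remaining arm fails at f = (24.2 − d)/115, and HR = ln(0.6)/ln(1 − f).

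| Outcome of the six if kept | d | f | HR, native tissue to colpopexy |
|---|---|---|---|
| None dropped (MITT) | – | 24.2/121 = 0.200 | 2.29 |
| None would fail | 0 | 24.2/115 = 0.210 | 2.16 |
| Fail at the arm's 20% | 1.2 | 23.0/115 = 0.200 | 2.29 |
| Fail at twice that rate | 2.4 | 21.8/115 = 0.190 | 2.43 |
| All would fail | 6 | 18.2/115 = 0.158 | 2.97 |

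**Effect on type I error.** Suppose there is no true difference, with 60% success in both arms. Dropping 6 women who were all failures raises success in the remaining mesh women to 72.6/115 = 63.1%, and the chance of rejection at nominal 0.01 to 0.025. If the six matched their arm, it stays at 0.010.

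**Consistency of the rationale.** The general rule in section 5 excludes switches that might bias the comparison against the null. Row 6 does not argue that. Its reason is that mixing the two mesh groups would make the estimates against native tissue harder to interpret. Under the design assumption of equal success in both mesh arms, a mesh-to-mesh switch is neutral, so keeping these women introduces no expected bias. Row 6 appeals to treatment received, yet rows 4 and 5 keep switchers as randomised, and the row 6 women themselves are kept in MITT for Aim 1a. Row 6 also says that outcomes in these switchers should be regarded as biased, which allows that they may differ from the rest of their arm.

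**The case against.** The best defence is that this is a disclosed and reasoned refinement, not a choice made after seeing results. The SAP says the populations were defined blind, without knowing which switches had occurred. MITT is a planned supportive analysis for Aims 2 and 3, fitted with the same model, and the listed displays include MITT, per-protocol and MITT-narrow. All of that stands, and it limits the consequence.

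Three stronger readings are tempting, and the documents do not support them:

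- A reader might infer that all surgeon-chosen crossovers are removed. Only switches between the two mesh operations are. Nor need every switch reflect findings at surgery, since the safety paragraph of section 5 also mentions refusal and accidental switching.
- A reader might infer that the two-woman fallback is data-driven because sizes are checked after unblinding. The threshold was fixed before unblinding, it is a simple count applied before any efficacy analysis, and when it operates it restores the protocol's population.
- A reader might infer that the exclusion favours mesh. That requires the dropped women to do worse than the rest of their arm, which nothing in the documents shows. They still received a mesh repair, and on the design assumption of 80% success in both mesh arms the expected shift is nil.

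It can also be said that MITT itself drops women after randomisation. It does, but failing to have surgery can occur in all three arms, whereas row 6 cannot touch the native tissue arm.

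Finally, SAP section 12 describes an analysis on the primary population and reports its proportional hazards result for MITT. That would fit the fallback having been used, but it is not proof, because MITT is also primary for Aim 1a.

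**Conclusion.** The protocol and SAP conflict on the primary population for Aims 2 and 3, and the SAP's choice adds a post-randomisation exclusion confined to the mesh arms. It can bias the comparison with native tissue either way. With an assumed 6 of 121 dropped from one arm, the hazard ratio of 2.29 could move to anywhere from 2.16 to 2.97. The two ends need none or all of the six to fail, so they are bounds, not expectations. Power is about 96% either way, so the exclusion gains no precision.

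The matter is live only if more than two women are affected in total, because otherwise the SAP reverts to MITT. It should be corrected, but it does not by itself show that either comparison is invalid: the departure is disclosed, it was set blind, and the MITT result is already planned.

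**What to change.** In SAP section 5 (Table 2, the Aims 2 and 3 text, and Table 3), make MITT the primary population for Aims 2 and 3 as Protocol M.2 states, with MITT-narrow and per-protocol supportive. The two-woman fallback then becomes unnecessary and can be removed.

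No new analysis is needed, since both are already planned and only their roles swap. Sample size and alpha are unchanged. However, SAP Version 2 (section 12) already cites event counts by arm, so this can no longer pass as a routine edit. Record it as a dated correction back to the protocol-specified population, state the number of colpopexy-to-mesh and mesh-to-colpopexy switchers in each arm, and report the MITT and MITT-narrow results side by side. Amending the protocol to match the SAP would remove the contradiction on paper but leave the one-sided exclusion in place.
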